#### 7.3.1 Reporting Procedures

Because this study involves minimal interaction between the research team and subjects, AEs and SAEs will most likely be identified through conversations with and reporting by clinical staff (providers & SWs) who provide direct care to enrolled subjects. Regular, monthly meetings with clinical staff will include dedicated questions to elicit whether any possible AEs or SAEs may have occurred.

AEs and SAE's will be recorded by the PI, research assistant immediately and the research team will conduct an analysis and determination of 1) whether or not the adverse event occurred, 2) the seriousness of the adverse event, 3) likelihood that the adverse event is associated with the intervention/study procedures; and 4) if necessary, preparation of report to the IRB and other entities.

Event	Action
Participant experiences inadequate symptom management or side effects from a therapy that is recommended by the PCC-PAC	Primary care team will be advised to make therapeutic adjustments.  Study team staff member completes alert form and provides to project manager and PI. A determination will be made by the person reporting the event, the PI

	and the study team jointly as to the extent to which the event is a consequence of the intervention.  Study team staff member monitors series of events.
Death Hospitalization Change in clinical status	Study team staff member completes alert form and provides to project manager and PI.  A determination will be made by the person reporting the event and the PI jointly as to the extent to which the event is a consequence of the intervention.  Monitor series of events in both groups to determine if rate is higher in the either group

- All adverse events that are both serious (SAE) and unexpected (i.e., have not been previously reported for the study's intervention) will be reported to the IMPACT Collaboratory Regulatory and Data Team Leader ([name] PhD), Advarra IRB, NIA IMPACT Collaboratory PO ([name]), and the IMPACT Collaboratory SO ([name]) within 48 hours of the study's knowledge of SAE.
- The summary of all other SAEs will be reported to IMPACT Collaboratory Regulatory and Data Team Leader ([name] PhD), Advarra IRB, NIA IMPACT Collaboratory PO ([name]), and the IMPACT Collaboratory SO ([name]) quarterly, unless otherwise requested by the SO.
- All deaths will be reported to IMPACT Collaboratory Regulatory and Data Team Leader ([name] PhD), Advarra IRB, NIA IMPACT Collaboratory PO ([name]), and the IMPACT Collaboratory SO ([name]) within 24 hours of study's knowledge of death.
- AEs will be reported per IRB policies and also to IMPACT Collaboratory Regulatory and Data Team Leader ([name] PhD), Advarra IRB, NIA IMPACT Collaboratory PO ([name]), and the SO ([name]) at minimum every 6 months, or at a frequency requested by NIA and/or by the SO.

#### Severity

- Mild: Awareness of signs or symptoms, but easily tolerated and are of minor irritant type causing no loss of time from normal activities. Symptoms do not require therapy or a medical evaluation; signs and symptoms are transient.
- Moderate: Events introduce a low level of inconvenience or concern to the participant and may interfere with daily activities, but are usually improved by simple therapeutic measures; moderate experiences may cause some interference with functioning
- Severe: Events interrupt the participant's normal daily activities and generally require systemic drug therapy or other treatment; they are usually incapacitating

#### Relatedness

- Definitely Related: The adverse event is clearly related to the investigational agent/procedure – i.e. an event that follows a reasonable temporal sequence from administration of the study intervention, follows a known or expected response pattern to the suspected

intervention, that is confirmed by improvement on stopping and reappearance of the event on repeated exposure and that could not be reasonably explained by the known characteristics of the subject's clinical state.

- Possibly Related: An adverse event that follows a reasonable temporal sequence from administration of the study intervention follows a known or expected response pattern to the suspected intervention, but that could readily have been produced by a number of other factors.
- Not Related: The adverse event is clearly not related to the investigational agent/procedure - i.e. another cause of the event is most plausible; and/or a clinically plausible temporal sequence is inconsistent with the onset of the event and the study intervention and/or a causal relationship is considered biologically implausible.

### **7.3.2 Follow-up for Adverse Events**

The occurrence of an adverse event (AE) or serious adverse event (SAE) may come to the attention of study personnel during conversations with providers/SWs.

All AEs not meeting the criteria for SAEs will be captured on the appropriate form. Information to be collected includes event description, time of onset, qualified medical professional's assessment of severity, relationship to (assessed only by those with the training and authority to make a diagnosis), and time of resolution/stabilization of the event. All AEs occurring while on study will be documented appropriately regardless of relationship. All AEs will be followed to adequate resolution.

Any medical condition that is present at the time that the participant is screened will be considered as baseline and not reported as an AE.

A study team member will record all reportable events with start dates occurring any time after study enrollment is obtained until 7 (for non-serious AEs) or 30 days (for SAEs) after the last day of study participation. Events will be followed for outcome information until resolution or stabilization.

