**Table 1. Telehealth PCC-PAC Encounter Protocol**

Steps	Actions/Content	Materials
1. Gather Information	- Discuss progress since admission with facility social work champion (e.g. improvement, stabilization, decline) - Elicit patient/family/staff input	 Electronic Health Record (EHR) PC note template  Video/tele conference
2. Patient Assessment	- Examine patient assisted by facility social work champion (subjective, objective assessments) - Conduct a comprehensive pain and symptom assessment	 EHR PC note template  Primary team notes  Video/tele conference

3. Goals of Care Conversation	
 
- Determine illness understanding/ treatment expectations
 
- Discuss initial transition planning after post-acute care
 
- Elicit goals; explore preferences for type and site of care
 
	 Advance care planning education  Communication scripts/guides  EHR PC note template  Video/tele conference
4. Document	
 
- Symptom assessment/management
 
- Propose treatment plan, ensure patient/family agreement
 
	 Symptom management protocols  EHR PC note template
5. Communicate	
 
- Communicate findings and recommendations to nursing and medical staff; determine agreement
 
- Determine if additional visit or meeting is needed
 
	 Preferred communication with primary care provider and staff  EHR PC note template
6. Follow up	
 
- Decide based on continued need for symptom assessment and management and ongoing goals of care discussions
 
	 EHR PC note template for follow up

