### 7.3 Adverse Events and Serious Adverse Events

**Adverse Event (AE):** AE is any untoward or unfavorable medical occurrence in a human study participant, including any abnormal sign (e.g. abnormal physical exam or laboratory finding), symptom, or disease, temporally associated with the participants' involvement in the research, whether or not considered related to participation in the research.

- PLWD experiences inadequate symptom management or side effects from a therapy that is recommended by the PCC-PAC

**Serious Adverse Event (SAE):** SAEs consist of any adverse event that results in death; is life threatening or places the participant at immediate risk of death from the event as it occurred; requires or prolongs hospitalization; causes persistent or significant disability or incapacity; results in congenital anomalies or birth defects; is another condition which investigators judge to represent significant hazards

Because this proposal involves an evidence-based palliative care intervention provided by specialty trained Nurse Practitioners, no serious adverse events are expected to occur. However, the following may occur in persons with serious illness:

- Death, Hospitalization, Change in clinical status

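### The baseline rule in section 7.3.2 makes no provision for worsening or persistence, so for symptoms already present at screening it conflicts with sections 7.3 and 7.3.1

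*Protocol*

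**What the plan says.** Section 7.3.2 sets the baseline rule: any medical condition "present at the time that the participant is screened will be considered as baseline and not reported as an AE". The same section limits recording to reportable events whose start date falls after enrolment, up to 7 days (non-serious) or 30 days (serious) after participation ends.

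Section 7.3 gives a broad general definition, "AE is any untoward or unfavorable medical occurrence in a human study participant", and one study-specific example: "PLWD experiences inadequate symptom management or side effects from a therapy that is recommended by the PCC-PAC". It defines serious events as a subset: "SAEs consist of any adverse event that results in death", followed by the other seriousness criteria, hospitalization among them. It also lists what may happen in seriously ill people: "Death, Hospitalization, Change in clinical status".

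The action table in section 7.3.1 has one row for the study-specific example and one for those three events. Both rows carry the same first reporting step: "Study team staff member completes alert form and provides to project manager and PI". Both also call for a joint judgement on whether the intervention caused the event. The bullets after the table govern reporting to the IRB, the NIA program officer and the safety officer: serious and unexpected events within 48 hours, other SAEs quarterly, all deaths within 24 hours, and AEs at least every 6 months.

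**The concern.** The intervention is a palliative consult, and one of its steps in Table 1 is "Conduct a comprehensive pain and symptom assessment". The symptoms such a consult sets out to manage will often have begun before the resident was screened. The event most specific to this intervention, a symptom that is not adequately managed, is therefore liable to fall on a condition that 7.3.2 classes as baseline and takes out of AE reporting.

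What is at stake is how far the safety record can be relied on. Under 7.2 the safety officer receives an interim and a final monitoring report. Under 7.3.1 events will mostly come to light through clinical staff and monthly meetings, so what is recorded depends on staff and study team applying one clear written rule. With two rules that disagree, the same clinical course could be an AE in one resident and baseline in another, and the reader of the report could not tell which rule had been used.

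**Working it through.** The point depends on no sample size, rate or test, and the protocol states no figure to reproduce. The check applies the rules to each kind of event in turn.

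| Event | Sections 7.3 and 7.3.1 | Section 7.3.2 | Result |
|---|---|---|---|
| Symptom present at screening, still uncontrolled after the consult | Inadequate symptom management: an AE, alert form | Baseline, not reported; original start date precedes enrolment | Conflict |
| Symptom present at screening that worsens without a serious outcome | Fits the general AE definition; alert form as a change in clinical status | Baseline, not reported; nothing says worsening sets a new start date | Conflict |
| Hospitalization for worsening of a known illness | Meets a seriousness criterion; alert form | Underlying condition is baseline; the admission itself starts after enrolment | Two readings possible |
| Symptom that begins after enrolment | AE | Rule does not apply | No conflict |
| Side effect of a therapy recommended at the consult | AE, alert form | Rule does not apply | No conflict |
| Death | All deaths reported within 24 hours | Does not alter that duty | No conflict |

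Three steps follow from the table.

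1. *The conflict in the first two rows.* The general definition in 7.3 neither names nor excludes worsening. The baseline sentence covers any condition and has no exception. The severity grades in 7.3.1 describe how bad an event is, but do not say that moving up a grade creates a new event. Nothing else in the protocol settles the matter.

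2. *The ambiguity in the third row.* An event must first be an AE to be an SAE. A reader who treats the admission as a new occurrence will report an SAE. A reader who treats it as part of a baseline condition has no AE and so no SAE. The text allows either.

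3. *Internal and external reporting differ.* The table's alert form goes to the project manager and the PI. The bullets that carry information outside the study team apply to AEs, SAEs and deaths. Deaths are reported whatever their classification. A hospitalization or a change in clinical status therefore produces an internal form in every case, but reaches the safety officer under these bullets only if it is classed as an AE or SAE.

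**The case against.** The strongest reply is that the gap is narrow and that other parts of the protocol cover most of it. The rule excludes a condition present at screening, whereas a hospitalization after enrolment is an event. The 7.3.1 table requires an alert form for hospitalization and for change in clinical status, with no exemption for known illness, and the second term comes close to a worsening provision. Hospitalizations are also collected at follow-up (6.2.3), named as the clinical outcome (9.4) and counted for each participant (9.5). No endpoint or stopping rule depends on AE counts in this single-arm pilot.

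Much of this stands, and it rules out several stronger inferences:

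- A reader might infer that the rule removes the only AE the protocol names. It does not. That example has two parts, and side effects of a recommended therapy arise after the consult. The other part is affected only for symptoms already present at screening.
- A reader might infer that most SAEs from known illness are lost, or that the safety record would be nearly empty. No figure supports either. Deaths are always reported, hospitalizations are reasonably read as new events, and new symptoms, like any other new untoward occurrence, remain AEs.
- A reader might infer that the screening window, Day -14 to Day -1, widens what counts as baseline. The rule fixes baseline at the time of screening, so a condition arising between screening and Day 0 is not baseline under it. Earlier screening tends to narrow the exclusion.

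The reply does not remove the conflict for symptoms present at screening, because the baseline sentence and the 7.3.1 table still give opposite instructions. Nor does counting hospitalizations as an outcome replace SAE reporting: section 9.5 attaches no relatedness judgement or reporting deadline to the count.

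**Conclusion.** The concern holds in a limited form. For a symptom present at screening that worsens or stays uncontrolled, 7.3.2 contradicts 7.3 and 7.3.1. Serious worsening of known illness is left open to inconsistent SAE classification, and reporting outside the study team, other than of deaths, follows that classification.

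The size cannot be given. The protocol does not say how many of the 30 residents will have symptoms at screening. Even that share would not count lost events, since only symptoms that are later inadequately managed or worsen matter. The conclusion assumes that 7.3.2 is applied as written; a team that already treats worsening as a new event would lose little, but the protocol does not tell it to do so.

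The implementation outcomes and the hospitalization count are unaffected. This is a reporting rule that should be corrected, but it does not undermine the trial's main results.

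**What to change.** Reconcile 7.3.2 with 7.3 and 7.3.1 by amending the baseline sentence to say that:

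- a condition present at screening is baseline only while it does not worsen;
- an increase in its severity or frequency after enrolment is recorded as an AE, with the date of the increase as the start date, so that the recording window applies to it;
- inadequate management of a symptom, including one present at screening, is recorded as an AE, as 7.3 and the 7.3.1 table already provide;
- an event that meets a seriousness criterion in 7.3 is an SAE even if the underlying condition was present at screening.

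The cost is a few sentences in an amendment, which goes to the IRB under 11.1, and somewhat more AE and SAE forms across 30 participants. The existing alert form serves. No new assessment or procedure is needed, and clinical care does not change.

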## **7.4 Safety Monitoring**

An NIA IMPACT safety officer will oversee study safety monitoring. The Principal Investigator will be responsible for ensuring participants' safety on a daily basis. In addition, the NIA-appointed SO will oversee all data and safety monitoring activities for this study. This SO will act in an advisory capacity to the NIA Director to monitor participant safety, to evaluate the progress of the study, and to review procedures for maintaining the confidentiality of data, the quality of data collection, management, and analyses. Advarra IRB will conduct the ethical review required for the protection of human subjects.

## **8 INTERVENTION DISCONTINUATION**

Subjects remain free to refuse the palliative care consultation and/or any care or therapies offered as a result of said consultation. Subjects may withdraw voluntarily from participation in the study at any time and for any reason. Participants should continue to be followed for 30 days, with their permission, even if the study intervention is discontinued.

If subject discontinued is due to an AE or SAE, every effort will be made to undertake protocol-specified safety follow-up procedures. If voluntary withdrawal occurs, the subject will be given appropriate care under medical supervision until the symptoms of any AE resolve or the subject's condition becomes stable.

## **9 STATISTICAL CONSIDERATIONS**

### **9.1 General Design Issues**

N/A

### **9.2 Sample Size and Randomization**

As this is a pilot clinical trial, the primary objective is to study the implementation outcomes to inform refinement of the intervention and modifications for a large-scale effectiveness trial. We anticipate 8-10 stakeholders will be required to achieve an understanding of the acceptability and appropriateness of the telehealth PCC-PAC and 30 PLWD to assess intervention fidelity and NH adoption of the telehealth PCC-PAC.

#### **9.2.1 Treatment Assignment Procedures**

All PLWD subjects will be assigned to the intervention.

### **9.3 Interim analyses and Stopping Rules**

An interim analysis is not planned.

### **9.4 Outcomes**

#### **9.4.1 Primary outcome**

**Implementation outcomes: acceptability, appropriateness, intervention fidelity, and NH adoption of the telehealth PCC-PAC**

**Clinical outcome:**

**Number of hospitalization(s)**

#### **9.4.2 Secondary outcomes**

N/A

### **9.5 Data Analyses**

**Stakeholder Engagement:** Interviews will be audiotaped and transcribed verbatim and managed and analyzed using NVivo 12.0. We will conduct initial descriptive data coding guided by directed content analysis techniques to describe the perceived most and least effective components of the intervention, barriers to implementation, and factors that facilitated the uptake, acceptance (adoption), and any adaptations of the intervention. We will then reorganize and condense coded data to compare similarities and differences and identify overarching categories. Categories will be grouped by their properties to develop themes. The study team will meet weekly during analysis to discuss codes, categories, and initial themes. The team will maintain a comprehensive audit trail, including methodological and analytic memos throughout the project.

**PLWD:** Intervention Implementation Fidelity (collaboration and implementation of findings from the PCC-PAC): Participating sites IT will provide deidentified reports to the study staff including each participants PCC-PAC notes and accompanying medical and treatment orders in the EHR. We

will quantitatively evaluate treatment delivery and treatment receipt using 90% adherence as a benchmark of success. Hospitalizations will be quantified for each participant

## **10 DATA COLLECTION AND QUALITY ASSURANCE**

### **10.1 Data Collection Forms**

The project manager or research assistant will collect clinical and demographic variables for eligible subjects from the EHR.

### **10.2 Data Management**

Study data will be entered and managed using NVivo 12.0 and REDCap (<http://www.project-redcap.org>) which is a secure, web-based application. The University of Maryland is a member of the REDCap consortium and this application is freely available to consortium members. REDCap provides: 1) an intuitive interface for data entry (with data validation); 2) audit trails for tracking data entry and changes; 3) automated export procedures for seamless data downloads to common statistical packages, 4) procedures for importing data from external sources; and 5) advanced features, such as branching logic and calculated fields.

### **10.3 Quality Assurance**

#### **10.3.1 Training**

To maximize quality control, the study team will be trained in all data collection and entry procedures. A designated team member will monitor data collection by checking completed data fields.

Quality Control Committee

N/A

#### **10.3.2 Metrics**

We will utilize double-data entry methods on a 10% random sample, with checks for discordant errors, and as data are entered into the REDCap system.

#### **10.3.3 Protocol Deviation**

Protocol deviations will be captured, documented, and reviewed by a member of the study team during interaction with providers and SWs. The PI will monitor deviations and the team will review each deviation for its root cause and assess whether a modification to the protocol is needed. Of note: PCC-PAC Intervention protocol adaptations will be tracked using a standard form.

#### **10.3.4 Monitoring**

The PI will monitor protocol compliance and data quality monthly with the study team.

## **11 PARTICIPANT RIGHTS AND CONFIDENTIALITY**

### **11.1 Institutional Review Board (IRB) Review**

This protocol and any subsequent modifications will be reviewed and approved by the Advarra IRB who is responsible for oversight of the study.

## Consent Procedure

Stakeholders: will provide verbal consent for participating in focus groups or semi-structured interviews using a script. The stakeholder who is a PLWD will be read the script for verbal consent to participate in the focus groups/semi structured interviews. The PLWD will then be asked what they understand about the purpose, the procedures, and the ability to refuse participation in the focus groups/semi structured interview at any time.

PLWD: We will seek a waiver of traditional informed consent for this study. A waiver of consent is permitted under 45 CFR provided the study meets the following requirements:

- The research involves no more than minimal risk to subjects;
- The waiver or alteration will not adversely affect the rights and welfare of subjects;
- The research could not practicably be carried out without the waiver or alteration;
- When appropriate, the subjects will be provided with additional pertinent information after participation

We will seek approval from the Institutional Review Board to conduct this pragmatic trial with a waiver of informed consent based on the following NIH Common Rule criteria: (1) palliative care consultation is standard of care and a low risk intervention; (2) the waiver will not adversely affect the rights and welfare of the subjects; hospice/palliative care and telehealth consults are already being offered in this site and this trial seeks to increase the opportunity for PLWD and their surrogates to benefit from telehealth palliative care consultation, while not restricting choice to forego it because it is not offered (3) The research cannot be practicably conducted without a waiver of the requirement for informed consent; the trial will evaluate system-level implementation of an evidence-based intervention; requiring prospective informed consent would introduce important selection biases greatly reducing the knowledge generated; and (4) to the extent possible, the subjects will be provided with pertinent information after participating in the trial.

PLWD subjects will be informed by the provider/SW that they are receiving a clinical evaluation via telehealth to discuss goals of care, symptoms, and any unmet needs associated with their illness. As this is a pragmatic clinical trial and the PCC-PAC is being integrated into the routine and usual care delivery of PLWD, the SW will use the same approach they use for other usual care delivery activities in the facility that address goals of care, symptoms, and unmet needs. Any of which the PLWD/surrogate decision maker will be informed that they can decline at any time.

